3.8 Justification of choice of study population

Genetic variability in genes encoding potassium channels are related to differences in working memory performance in healthy young subjects (Heck, Fastenrath et al. 2014). We therefore decided to investigate the effects of fampridine on working memory in healthy young subjects.

4 STUDY OBJECTIVES

4.1 Overall Objective

The overall objective of this study is to evaluate if fampridine has an influence on cognitive functions in healthy young participants.

4.2 Primary Objective

The primary objective of this study is to evaluate if fampridine has an influence on working memory in healthy young participants.

4.3 Secondary Objectives

The secondary objectives are to assess the influence of fampridine on different working memory functions, attention, processing speed, fluid intelligence and resting motor threshold (rMT).

4.4 Safety Objectives

The study aims to assess tolerability of study medication in terms of incidence of side effects e.g. headache, gastrointestinal discomfort and dizziness and the rate of AEs.

5 STUDY OUTCOMES

5.1 Primary Outcome

- High-load working memory performance (3-back (d')) as assessed by a letter n-back task) after repeated intake of study medications (visit 3 and 5).

5.2 Secondary Outcomes

- High-load working memory performance (3-back (d')) as assessed by a letter n-back task) after acute intake of study medication (visit 2 and 4)
- rMT measurement using TMS after repeated intake of study medication (visit 3 and 5)

Performance in other working memory-related tasks and other n-back outcomes after acute and repeated intake of study medication

- Reaction time (for correct 3-back responses)
- Performance in a 0 back task as a measure of attention
- Symbol Digit Modalities Test, SDMT (Smith 2013, 13th edition)
- BOMAT - advanced (Hossiep/Turck/Hasella, 1999)
- Digit span forward and backward performance (von Aster 2006)

5.3 Safety Outcomes

- Headache, dizziness and gastrointestinal discomfort (see chapter 10.1.1) will be recorded and rated by the participants using visual analogue scales.
- AE-recording
- Vital signs

5.4 Assessment of potential confounders

- Tiredness and motivation will be rated by the participant using visual analogue scales.

6 STUDY DESIGN

6.1 General study design and justification of design

Pharmacological proof-of-concept study on the effects of 10 mg fampridine (twice daily oral administration) on physiological processes, in particular working memory, in healthy participants using the following design:

- randomized
- double-blind (participant, study team)
- placebo-controlled
- cross-over
- counter-balanced

The duration of the study from first participant in to last participant out is approx. 24 months. Duration for an individual study participant will be at most 7 to max. 15 weeks, depending on the duration of the wash out period.

There will be two intervention periods of 3.5 days during which medication (fampridine /placebo) will be applied separated by a wash out period of 8 (days between Visit 3 and Visit 4; equivaling over 30 half-lives of the study drug) up to 82 days (12 weeks).

Two test days will take place during each intervention period: one on the first day and one on the last day of each period during which cognitive functions under the influence of fampridine/placebo will be assessed using parallel versions of tests.

At the beginning of test day 1 (visit 2), each subject will be randomized to receive either placebo or fampridine first.

After the administration of study medication (visits 2-5) there will be a 4-h waiting period allowing the medication to reach peak cerebrospinal fluid levels (Hayes 2004). After this time period, the cognitive test battery will be administered.

At the end of each visit, participants will be asked about their actual wellbeing. If there are no complaints or symptoms, participants can be dismissed. In case of minor health problems, the participant will have to stay in the study center until recovery under medical supervision. In case of more severe incidents staff acts according to chapter 10.4.6.

The study will end for the subjects in the evening of the second test day of the second intervention period (visit 5). The duration for the different study parts see table 1 (Duration of Study parts, page 12).

6.2 Methods of minimizing bias

To minimize bias, participants will be randomly allocated to treatment groups (e.g. starting with fampridine or placebo) and study will be double-blinded.

6.2.1 Randomization

After pre-examination on visit 2, each participant will be assigned to a randomization number. Each eligible participant will be allocated to one of the two randomization groups (Placebo/Verum or Verum/Placebo) according to the maximum tolerated imbalance (MTI) procedures. This allocation will be generated automatically by secuTrial®. This procedure ensures that participants will be randomly allocated to the two groups, while accounting for sex as a covariate of potential importance.

The replacement of all Drop-Outs will be carried out after assignment of all 44 medication kits is completed. There will be replacement of Drop-Outs until data of approximately 44 participants are completed.

6.2.2 Blinding procedures

The IMP and the placebo are identically looking tablets to ensure double-blind conditions.

The pharmacy will prepare one kit of study medication per participant. Each kit will consist of two intransparent plastic containers, each containing either seven tablets of blistered fampridine and a drying agent or unblistered placebo and a drying agent. It is necessary to keep Fampyra® blistered as long as possible to prevent any contact of fampridine with humidity. After unblistering Fampridin® will stay stable

for seven days in a closed container while adding a drying agent (professional / prescribing information Germany Fampyra® SR). Each kit of study medication will be labelled with a randomization number. A staff member not involved in the conduct of the study will open the kit and the plastic container corresponding to the respective intervention period in a separate room. If Verum is inside he will unblister all the verum tablets and hand over the first tablet to the subject, who is waiting in a different room. If Placebo is inside the staff member may directly hand over the first tablet to the subject, who is waiting in a different room. Afterwards the subject will be handed over the reclosed container for the intake of the study medication at home. During each intervention period a tablet must be taken every 12 hours for 5 times at home. The last (7th) intake of the study medication will be again in the study center. Therefore, the subject must bring along the container including the last tablet at the second study day of each intervention period.

6.2.3 *Other methods of minimizing bias*

The investigators of the test days will be trained and will follow detailed working instructions to ensure that each test day will be conducted in a highly standardized way.

Study team members involved in testing, data acquisition or data analysis are blinded. The study team member preparing the IMP at the testing days has no other outcome-related tasks in the study.

The administration of medication will take place at the same time frame (8-9 a.m.) for each participant. Testing will take place in the same location at the premises of the Division of Cognitive Neuroscience of the University of Basel for each participant and during the same time of the day to minimize the influence of diurnal differences in cognitive test performance.

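### The staff member who learns the allocation gives the participant the first tablet of each period, after preparation that differs by arm: a limited but avoidable cue at 2 of 14 intakes

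*Combined protocol and SAP*

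**What the plan says.** Section 6.1 lists the design as "double-blind (participant, study team", that is, both parties are blinded. Section 6.2.2 relies first on appearance: "The IMP and the placebo are identically looking tablets to ensure double-blind conditions". The packaging inside the opaque containers differs, however, "each containing either seven tablets of blistered fampridine and a drying agent or unblistered placebo and a drying agent". The reason given is that fampridine must be kept from humidity for as long as possible.

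On the first test day of each period, "A staff member not involved in the conduct of the study will open the kit" and the container "corresponding to the respective intervention period in a separate room". The next step depends on what is found. For verum: "If Verum is inside he will unblister all the verum tablets and hand over the first tablet to the subject". For placebo: "If Placebo is inside the staff member may directly hand over the first tablet to the subject". In both cases the participant is waiting in another room and then receives the reclosed container to take home.

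Section 6.2.3 adds that team members who test, acquire data or analyse are blinded, and that "The study team member preparing the IMP at the testing days has no other outcome-related tasks in the study". Section 8.4 refers the reader to a chapter 7.6 for blinding, but the contents list ends chapter 7 at 7.5, so that pointer leads to no further description.

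**The concern.** Opening the container reveals the treatment, and the person who opened it then meets the participant. That person's manner can carry information without any intention. If verum is given only after all tablets have been unblistered and placebo is given straight away, the waiting time can carry it too. The text describes no sham step, no equalised preparation time and no blinded intermediary.

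Any such cue is tied to treatment and not to period, so randomising the order does not average it out. The mixed model in section 11.4 compares verum with placebo and cannot separate an expectancy effect from a drug effect. Cognitive scores depend partly on effort, and the plan itself treats motivation as a potential confounder (5.4, 11.4.2). Headache, gastrointestinal discomfort and dizziness are rated by the participant on visual analogue scales and are left out of ordinary adverse event recording (10.1.1). The text describes no question asking participants to guess their treatment, so a leak would go unnoticed.

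**Working it through.** **1. Contacts with the informed person.** Section 6.2.2 gives the intakes per period: one handed over at the first test day, five at home, and a seventh at the centre from the container the participant brings back.
- Intakes per participant: (1 + 5 + 1) × 2 periods = 14.
- Intakes handed over by the preparer: 1 × 2 = 2, so 2 of 14.
- Across 44 completers: 44 × 2 = 88 hand-overs.

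No opening, unblistering or hand-over by the preparer is described for visits 3 and 5.

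**2. Time from hand-over to assessment.** Inputs: 12 h between tablets (6.2.2, 8.1.1) and testing 4 h after intake (6.1).
- Acute secondary outcomes, visits 2 and 4: 4 h after the first tablet. Symptom ratings on those days fall just before testing and at the end of the visit.
- Primary outcome, 3-back d' at visits 3 and 5: the seventh tablet comes (7 − 1) × 12 = 72 h after the first, and testing is at 72 + 4 = 76 h.

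**3. What each safeguard covers.**

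| Safeguard | Covers | Does not cover |
|---|---|---|
| Identical tablets | Appearance of the dose | Manner of the person giving it |
| Separate room, opaque reclosed container | Sight of the unblistering | Length of the wait |
| Blinded testers and analysts | Outcome assessment and analysis | Participant expectancy |
| Preparer has no other outcome-related task | Scoring by an informed person | The hand-over itself |

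Each safeguard is useful, but none covers the moment of hand-over.

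**4. Who counts as blinded.** Section 6.1 blinds the study team. Section 6.2.2 places the preparer outside the conduct of the study, while 6.2.3 calls the same person a study team member. If 6.2.3 is right, the statement in 6.1 is not literally true. If 6.2.2 is right, an outsider to the trial doses its participants.

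**5. Size.** The plan's only related figure is its sample size (11.2): paired two-sided t-test, dz = 0.5, α = 0.05, 90% power. With df = N − 1 and noncentrality dz × √N, N = 44 gives power 0.9000 and N = 43 gives 0.8931. The smallest adequate N is 44, as stated, and this point does not alter it.

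The same formula shows what a spurious shift would do if the drug had no effect. The shifts, in SDs of the paired difference, are assumptions and have no source in the documents.

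| Assumed shift | Noncentrality (shift × √44) | Chance of p < 0.05 |
|---|---|---|
| 0 | 0 | 5.0% |
| 0.05 | 0.33 | 6.2% |
| 0.10 | 0.66 | 9.9% |
| 0.15 | 0.99 | 16.3% |
| 0.20 | 1.33 | 25.4% |

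The table shows sensitivity only. It does not say which row, if any, applies.

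**The case against.** The case for the plan is strong in several places. The unblistering takes place out of the participant's sight, so a reader who infers that the two preparations are visibly different goes beyond the text. The plan discloses its one informed role, restricts that role and keeps testers, data acquisition and analysis blinded. A reader might also infer that the trial is therefore not double-blind, but the documents do not show that any participant or tester learns the treatment.

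The cue itself is only possible. The documents do not say how long unblistering takes, whether the same person serves both periods, or whether participants know when preparation starts. Immediate hand-over of placebo is permitted, not required. The two hand-overs lie well apart, since the wash-out between visits 3 and 4 is 8 to 82 days. The test-day working instructions mentioned in 6.2.3 are not part of the document and may already standardise the step. An effect on the primary outcome would have to last about three days and, to favour fampridine, run consistently in that direction.

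There is also a practical objection. Routing the tablet through the test-day investigator could move the cue from the participant to someone who scores outcomes.

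Most of this stands and limits the point. It does not remove it: an informed person meets the participant at the first dose of both periods, the written steps differ by arm, and the humidity rationale explains the blister but not who must do the hand-over. The practical objection is met by a transfer without contact.

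**Conclusion.** The point holds in a limited form. Section 6.2.2 leaves two avoidable cues, the behaviour of an informed person and a possible difference in waiting time, at 2 of 14 intakes per participant. This weakens participant blinding and leaves assessor blinding intact. The risk is nearest to the acute secondary outcomes and the same-day symptom ratings, and more remote for the primary outcome.

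The count and the timing follow from the documents, assuming tablets are taken at the stated 12 h interval. The size of any bias cannot be estimated. A reader might take the rise from 5% to 25% in the table as the inflation of the false-positive rate, but it rests wholly on assumed shifts and should not be cited as the trial's error rate. Likewise, the 88 hand-overs are contacts and not instances of unblinding. The change is worth making because it lowers a bias risk, in a cross-over with effort-dependent and self-rated outcomes, at little cost.

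**What to change.** - **Same preparation in both arms.** In 6.2.2, require the same sequence of steps and the same fixed preparation time for verum and placebo, with a matching step where placebo needs no unblistering. Packaging stays as it is.
- **No contact with the informed person.** The preparer leaves the first tablet in a neutral cup, with the reclosed opaque container, at a set place, and meets neither the participant nor the tester. A blinded team member collects both and gives them to the participant.
- **One description of the role.** Align 6.1, 6.2.2 and 6.2.3: one named unblinded role, with the rest of the study team blinded. The pointer in 8.4 can be corrected at the same time.
- **Clean start.** Version 7 is dated 05/04/2022 and the first participant was planned for 09/2021, so recruitment may have begun. Apply the change from a documented date, and only to participants who have not started period 1, so that both periods of any one participant follow the same procedure.

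The cost is a few minutes' wait on placebo days, one more entry in the accountability log and, if recruitment has begun, a recorded mid-trial change in procedure. No new packaging is needed. Section 6.2.3 already provides for blinded team members, though the documents do not give the staffing of each test day.

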6.3 Unblinding Procedures (Code break)

Unblinding will be permitted under these circumstances

- SAE
- AE if knowledge is crucial for further medical approach

The investigator or a representative can perform the unblinding of the participant at any time. To ensure that unblinding is possible at any time, there is a unblinding procedure implemented in secuTrial®. The investigator or a representative will report to the sponsor-investigator and document the unblinding. Not involved study team members will not be informed about the result.

7 STUDY POPULATION

7.1 Eligibility criteria

Participants fulfilling all of the following inclusion criteria are eligible for the study:

- male or female
- generally healthy
- normotensive (BP between 90/60mmHg and 140/90mmHg)
- BMI between 19 and 29,9 kg/m²
- aged between 18 and 30 years
- fluent German-speaking
- IC as documented by signature
- At least double vaccination against Covid-19

The presence of any one of the following exclusion criteria will lead to exclusion of the participant:

- contraindications to the class of drugs under study, e.g. known hypersensitivity or allergy to 4-aminopyridine
- use of potassium channel blockers within the last 3 months
- concomitant treatment with OCT 2 inhibitors and -substrates (e.g. cimetidine, propranolol)
- acute or chronic psychiatric disorder (e.g. major depression, psychosis, somatoform disorder, suicidal tendency)
- acute cerebrovascular condition
- history of seizures
- risk of lowered seizure threshold (due to e.g. sleep deprivation, withdrawal of alcohol after alcohol abuse)
- renal impairment
- history of malignant cancers
- walking problems (e.g. due to dizziness)
- other clinically significant concomitant disease states (e.g. hepatic dysfunction, cardiovascular disease, diabetes, asthma,
- bradycardia < 50/min during clinical examination
- clinically significant laboratory or ECG abnormality that could be a safety issue in the study
- known or suspected non-compliance (e.g. missing more than one dose of study medication per intervention phase)
- drug or alcohol abuse
- inability to follow the procedures of the study, e.g. due to language or psychological problems of the participant
- participation in another study with an investigational drug within the 30 days preceding and during the present study
- prior participation (less than two years ago) in a study investigating working memory (notably the n-back task)
- enrolment of the investigator, his/her family members, employees and other dependent persons
- smoking (>3 cigarettes per day)
- intake of psychoactive drugs (e.g. benzodiazepines, antidepressants, neuroleptics)
- pregnancy or breast feeding
- experiencing a syncope during basal rMT measuring

Exclusion Criteria concerning TMS measurement

- metal in the brain, skull or elsewhere in the body (e.g., splinters, fragments, clips, etc.)
- implanted neurostimulator (e.g., DBS, epidural/subdural, VNS)
- cardiac pacemaker or intracardiac lines
- medication infusion device
- piercings, pivot teeth (retainers are no exclusion criterion)
- tattoos (head area) less than 3 months old or older than 20 years
- condition after neurosurgery
- hearing problems or tinnitus

- not able to sit still due to tremor, tics, itching
- History of repeated syncope
- head trauma diagnosed as concussion or associated with loss of consciousness
- diagnosis of epilepsy, or a convulsion or a seizure in the past of the participant or his family
- TMS in the past showing problems
- MRI in the past showing problems
- surgical procedures to spinal cord
- spinal or ventricular derivations

Remark: It is necessary to ensure that the metal nose piece of surgical masks, if they have to be worn as protection against Covid-19 infection, is not ferromagnetic (Bikson, Hanlon et al. 2020).

7.2 Recruitment and screening

Study participants will be searched in the German speaking part of Switzerland using the following websites mcn.unibas.ch and markt.unibas.ch,.

We may also invite former participants of unrelated studies of the Divisions of Cognitive and Molecular Neuroscience interested in further study participation by e-mail.

After contacting us, the interested person will be sent the “Participant information and informed consent form” together with some administrative information. If the person is still interested in participating, a study team member will call the interested person to inform him/her about the study and answer his/her questions. Afterwards, a pre-screening with a check of the main in- and exclusion criteria will be performed. If the interested person meets all inclusion criteria and none of the exclusion criteria and is interested in participating, the screening visit will be fixed.

All interested persons will be advised not to come to the study center in case of common cold or flu like symptoms but fix an alternative date. The telephone screening documents will be filed as part of the Source Data (SD) in the participant's dossier. The telephone screening documents of participants not eligible for a study participation will be shredded. All steps will be documented and we will assess the number of participants, who were not eligible during pre-screening.

For screening procedures see chapter 9.4.1.

A study compensation of CHF 800 including travel expenses will be paid at the end of the second test period. Screening Failures and Drop-Outs receive a pro rata temporis compensation.

7.3 Assignment to study groups

After informed consent, each participant will be assigned to a participant number. Then, eligible participants will be allocated to the treatment group (i.e. either fampridine or placebo first) following the order of the randomization list. The randomization number will be listed in the SD, in the eCRF and in the Drug Accountability Log.

7.4 Criteria for withdrawal / discontinuation of participants

Participants have the right to withdraw from the study at any time for any reason without being obliged to give reason. There will be a final examination after withdrawal for whatever reason. The investigator also has the right to withdraw participants from the study if it is in the best interest of the participant.

The following reasons result in withdrawal:

- Adverse events challenging the health of the participant if continuing the study
- Adverse events prohibiting cognitive testing or rMT-measurement, e.g.
 - headache, dizziness and nausea more than mild or
 - having slept less than 4 hours during the last night (Visits 3 and 5).
- Participant being ill at ease during rMT measuring
- Intake of psychoactive substances within 3 days before test days (e.g. benzodiazepines, antidepressants, neuroleptics, cannabis)
- Non-Compliance
- Severe protocol violations
- Administrative troubles
- Positive pregnancy test (test day 1 or test day 3)

- Alcohol intake within 12 hours before start of all visits

Withdrawal date and reason will be listed in the participant enrolment log. Safety data will be analyzed for all participants, who received at least one dose of study medication. There will be no anonymization of the data. For information about data handling see chapter 12.3.

